In the single arm trial of ixabepilone monotherapy patients with measurable disease who had tumor progression while receiving prior anthracycline, taxane, and capecitabine were enrolled. Ixabepilone 40 mg/m^2 monotherapy was administered as a 3-hour intravenous infusion on day 1 of a 21-day cycle. The primary end point was objective response rate (ORR), assessed by an independent radiology facility (IRF). A total of 126 patients were treated and 113 were assessable for response. Patients were heavily pretreated with 88% having received at least two lines of prior chemotherapy in

the metastatic setting. IRF-assessed ORR was 11.5% (95% CI, 6.3% to 18.9%) for response-assessable patients. Investigator-assessed ORR for all treated patients was 18.3% (95% CI, 11.9% to 26.1%). Fifty percent of patients achieved stable disease (SD); 14.3% achieved SD  $\geq$  6 months. Median duration of response and progression-free survival were 5.7 and 3.1 months, respectively. Median overall survival was 8.6 months. Patients received a median of 4.0 treatment cycles (range, one to 16 cycles), and 25% of patients received  $\geq$  eight cycles. Grade 3/4 treatment-related events included peripheral sensory neuropathy (14%), fatigue/asthenia (13%), myalgia (8%), and stomatitis/mucositis (6%). Resolution of grade 3/4 peripheral sensory neuropathy occurred after a median period of 5.4 weeks. The authors concluded that ixabepilone demonstrated clear activity and a manageable safety profile in patients with MBC resistant to anthracycline, taxane, and capecitabine. Responses were durable and notable in patients who had not previously responded to multiple prior therapies.

Ixabepilone has also been evaluated in the neoadjuvant setting [58]. That study was designed to determine the pathological response obtained with ixabepilone as neoadjuvant therapy for breast cancer and to obtain tumor samples for analysis of gene expression and identification of potential predictors of response to ixabepilone. Based on the genomic study, patients with hormone receptor–negative disease were more likely to respond to ixabepilone [58].

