## 5 DATA COLLECTION and EVALUATION

### 5.1 DATA COLLECTION AND RECORD KEEPING

Data will be prospectively collected and entered into the database at least once every two weeks. The NCI C3D database will be used for this report. The responsible investigator is [name]. All radiographic images will be stored in the Department of Radiology, Clinical Center, NIH. All radiographic images will be reviewed by a staff radiologist for validity and reliability. The original signed consent goes to Medical Records; copy placed in research record

All patients must have signed an informed consent and an on study confirmation of confirmation of eligibility form must be filled out before enrollment.

Complete records must be maintained on each patient. These will consist of the hospital chart with any supplementary information obtained from outside laboratories, radiology reports, or physician's records. These records will serve as the primary source material that forms the basis for the research record. All relevant data will also be entered into the NCI C3D database from which formal analyses are done. The primary source documentation will assure the following: on study information, including patient eligibility data and patient history; and off-study summary sheets, including a final assessment by the treating physician.

Data will be submitted to the CTEP/CDUS every three months via the NCI C3D database.

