- In the case of SD, follow-up measurements must have met the SD criteria at least once after study entry at a minimum interval, not less than 6 weeks.

Duration of overall response:

- The duration of overall response is measured from the time measurement criteria are met for CR or PR (whichever status is recorded first) until the first date that recurrence or PD is objectively documented, taking as reference for PD the smallest measurements recorded since the treatment started.

Duration of stable disease:

- SD is measured from the start of the treatment until the criteria for disease progression are met, taking as reference the smallest measurements recorded since the treatment started.

Response review:

- Responses will be reviewed by an expert(s) independent of the study at the study's completion. Simultaneous review of the patients' files and radiological images will be conducted.

Reporting of results:

- All patients initially considered evaluable will be assessed for response to treatment, even if there are major protocol treatment deviations or if they are ineligible. Each patient will be assigned one of the following categories: 1) complete response, 2) partial response, 3) stable disease, 4) progressive disease, 5) early death from malignant disease, 6) early death from toxicity, 7) early death because of other cause, or 8) unknown (not assessable, insufficient data).
- All of the patients who met the eligibility criteria and are evaluable, will be included in the main analysis of responses. Patients in response categories 4-8 will be considered as failing to respond to treatment (disease progression). Thus, an incorrect treatment schedule or drug administration will not result in exclusion from the analysis of a response.
- All conclusions will be based on all eligible patients.
- Sub-analyses may be performed on the basis of a subset of patients, excluding those for whom major protocol deviations have been identified (e.g., early death due to other reasons, early discontinuation of treatment, major protocol violations, etc.). However, these sub-analyses may not serve as the basis for

drawing conclusions concerning treatment efficacy, and the reasons for excluding patients from the analysis will be clearly reported.

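### The independent response review is read with the patient file open, so it is not protected from anchoring on the investigator's call, and the plan does not say whether its result feeds the 4-of-37 rule

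*Combined protocol and SAP*

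**What the plan says.** Under Response review, Section 5.2 has one or more experts from outside the study look at responses once the study is complete. It then specifies the material: "Simultaneous review of the patients' files and radiological images will be conducted". It does not set an order of reading, does not withhold the site's measurements or response call, and does not say how a disagreement is settled.

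Section 5.1 describes the patient record: "These will consist of the hospital chart with any supplementary information obtained from outside laboratories, radiology reports", and physicians' records. The source documentation also holds "off-study summary sheets, including a final assessment by the treating physician". The same section adds another look at the scans: "All radiographic images will be reviewed by a staff radiologist for validity and reliability". That reader is not described as masked or as independent of the study.

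Section 5.2 asks for PR and CR to be confirmed at least 4 weeks later and gives overestimation of response as the reason. Section 5.4 defines the primary endpoint as PR+CR by RECIST. Section 5.4.1 declares a cohort active at 4 or more responses in 37. Neither names the assessor whose call is counted.

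**The concern.** The trial is open and single-arm, and each cohort's conclusion rests on a count of four. Partial response depends on a 30% fall in a sum of diameters over chosen lesions, which leaves judgement at the margin. An outside read is the natural protection. Its value depends on the reader forming a view before learning what the treating team concluded.

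Here the plan prescribes the opposite order, or at least no order: file and images together. A reader who has the site's reports and final assessment in hand may be drawn towards ratifying them, so some over-called responses could survive the review. If they are counted, the chance of declaring an inactive drug active rises above the planned 0.10. If the reviewed result is not what is counted, the review protects no decision at all, and the plan leaves that open.

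**Working it through.** **Passages side by side.** Section 5.2 gives the expert the patients' files together with the images. Section 5.1 says the records contain radiology reports and the treating physician's final assessment. No section removes these before the review. Exposure to the site's call is therefore the natural reading, but it is an inference from two sections and not a stated procedure.

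**Inputs (Section 5.4.1).** p0 = 0.05, p1 = 0.20, alpha = beta = 0.10. Stop a cohort at 0/12; otherwise continue to 37; active at 4 or more. Stated early-termination probability under p0: 0.54.

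**Formula.** With X37 ~ Bin(37, p), X12 ~ Bin(12, p) and Y25 ~ Bin(25, p):

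P(active) = P(X37 ≥ 4) − P(X12 = 0) × P(Y25 ≥ 4)

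The second term removes cohorts that would have reached 4 but were stopped at 0/12.

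**Reproducing the plan.**
- Early stopping under p0: 0.95^12 = 0.540, as stated.
- Type I error: 0.1119 − 0.5404 × 0.0341 = 0.0935.
- Power at 20%: 0.9550 − 0.0687 × 0.7660 = 0.902.

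The design figures are correct. The margin below 0.10 is 0.0065.

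**Sensitivity to over-calling.** Let f be the share of true non-responders who are counted as responders after every check. This is an assumption; no value is in the documents. True responders are taken as all correctly called. Under the null, the counted rate is q = 0.05 + 0.95f.

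| f | q | P(stop at 0/12) | P(active) |
|---|---|---|---|
| 0 | 0.0500 | 0.540 | 0.0935 |
| 1% | 0.0595 | 0.479 | 0.1760 − 0.4790 × 0.0583 = 0.148 |
| 2% | 0.0690 | 0.424 | 0.2502 − 0.4240 × 0.0899 = 0.212 |

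**Does the assessor matter for this drug?** Section 1.2.4 cites a single-arm breast-cancer trial of ixabepilone. Its independent result: "IRF-assessed ORR was 11.5% (95% CI, 6.3% to 18.9%) for response-assessable patients", with 113 patients assessable. Its investigators reported 18.3% of 126 treated patients. Back-calculated counts are 0.115 × 113 ≈ 13 and 0.183 × 126 ≈ 23. The two readings differ, on different denominators.

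**The case against.** **Files have a proper use.** Superficial clinical lesions can be measurable disease, non-target CR needs the tumor marker level, and a doubtful CR may rest on aspirate or biopsy. An expert confined to images could not apply Section 5.2 in full. This stands. It argues for a controlled second step, not for opening everything at once.

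**Other safeguards exist.** A staff radiologist reviews all images, and PR/CR must be confirmed at 4 weeks or more. Both should reduce over-calling. Neither is described as masked to the site's call, so neither replaces an unanchored read.

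**A reader might infer that the expert is certain to see the investigator's response call and that the review is worthless as a check.** The documents do not go that far. They do not list what is handed to the expert or call the final assessment a RECIST verdict, and the expert is independent of the study and has the images.

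**A reader might also scale the null rate by the cited trial's gap.** Ratios of 18.3/11.5 = 1.59 or 23/13 = 1.77 would put a true 5% at 7.95% or 8.85%, and P(active) at 0.29 to 0.36. That does not measure this problem. The gap is investigator against independent reading, not open-file against masked reading. It comes from another tumor and schedule and mixes treated with assessable patients. It would also require this trial's reviewer to correct nothing.

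**Finally, the wording could suggest that only claimed responses go to review.** The text does not settle that.

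**Conclusion.** The concern holds in a limited form. Section 5.2 prescribes a simultaneous read of file and images, Section 5.1 puts the site's reports and final assessment in the record, and nothing shields the expert from them. The review is thus unprotected from anchoring, which is less than saying that it is biased. The missing link to the decision rule is part of the same defect, because an unanchored read changes a conclusion only if it is the read that counts.

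No design figure in the plan is wrong. The size is an illustration: per-cohort type I error moves from 0.0935 to 0.148 or 0.212 if 1% or 2% of true non-responders stay over-called in the final data. How much of any over-calling the open file would preserve cannot be estimated from the documents. The cited 18.3% and 11.5% show only that the assessor can matter. The change is worth making because it is cheap and the threshold is four responses.

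**What to change.** Replace the simultaneous-review sentence in Section 5.2 with a two-step read by the same expert.

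1. The expert reads the baseline and restaging images without the site's response call, measurements, radiology reports or off-study sheet, then records and locks a response.
2. The file is opened only for data the criteria need: superficial clinical lesions, tumor markers, and cytology or biopsy. Any change to the locked response is recorded with its reason.

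Include some patients whom the site did not call responders, so that being in the review does not reveal the call. The number and selection can be left to the sponsor.

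In Section 5.4.1, state that this result, with its recorded changes, feeds the final 4-of-37 count, and report the investigator-assessed rate beside it. A review at study completion cannot inform the 0/12 decision, so the plan should also say whose call is used there. Even if stage 1 never stopped a cohort, a final count with a true 5% rate and no over-calling would give P(X37 ≥ 4) = 0.112, so most of the protection lies in the final read.

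The cost is protocol wording, preparation of image sets without site annotations (including any scans sent in by local physicians), and modest reading time. No patient, scan or reader is added. The reported response rate may come out lower.

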### 5.3 Toxicity Criteria: Adverse Event Reporting Criteria

The following adverse event management guidelines are intended to ensure the safety of each patient while on the study.

The descriptions and grading scales found in the revised NCI Common Terminology Criteria for Adverse Events (CTCAE) version 3.0 will be utilized until December 31, 2010 for AE reporting. CTCAE version 4.0 will be utilized beginning January 1, 2011. All appropriate treatment areas should have access to a copy of the CTCAE version 4.0. A copy of the CTCAE version 4.0 can be downloaded from the CTEP web site (<http://ctep.cancer.gov>).

### 5.4 STATISTICAL SECTION

#### STUDY OBJECTIVES:

Primary: To establish the activity of ixabepilone administered daily as a one-hour infusion on five successive days (daily x 5), every three weeks in patients with cervical carcinoma previously treated with chemotherapy, as determined by overall response (PR+CR). Activity will be measured using standard RECIST guidelines.

Secondary: Assess pharmacodynamic endpoints after ixabepilone administration to determine the extent of tubulin polymerization and whether or not there has been activation of cellular death pathways “distal” to the target, and to estimate the progression free survival and duration of response.

#### 5.4.1 Trial Design:

This trial of Ixabepilone in patients with cervical carcinoma will be conducted using a two-stage optimal design (Simon, R, Controlled Clinical Trials, 10:1-10, 1989). With  $\alpha = 0.10$  (the probability of incorrectly accepting a poor agent), and  $\beta = 0.10$  (the probability of incorrectly rejecting a good agent), we will try to rule out an undesirably low overall response (PR+CR) probability of 5% ( $p_0 = 0.05$ ) in favor of a level indicative of modest activity, 20% ( $p_1 = 0.20$ ).

Several histologic subtypes of cervical carcinoma are recognized including: (1) squamous cell (2) adenocarcinoma (3) adenosquamous carcinoma and (4) other. Among these, squamous is the most common histologic diagnosis, with adenocarcinoma second in frequency. While chemotherapy has not been shown to be very effective in cervical carcinoma, differences among the histologic subtypes in response to therapy may exist. In order to properly evaluate the activity of ixabepilone in cervical cancer, we will stratify patients into two cohorts according to histologic subtypes: (1) squamous cell (2) non-squamous including adenocarcinoma, adenosquamous carcinoma and non-squamous-not otherwise specified.

Initially, 12 evaluable patients will be enrolled in each of the two cohorts. If 0/12 demonstrate an objective response (PR +CR), then accrual to that cohort will stop and the agent will be considered inactive in this population. If one or more patients have a response, accrual will continue until a total of 37 evaluable patients have been enrolled in that cohort. If 1 - 3 of 37 patients demonstrates a response in a cohort, this will be

considered insufficient activity, and the agent will not be considered worthy of further development in that cohort. If 4 or more of 37 patients in the entire cohort have a response, then the agent will be considered active in that group (and at least potentially able to produce a response level consistent with 20%). Under the null hypothesis ( $p_0 = 0.05$ ), the probability of early termination of accrual to any one group is 0.54. With two cohorts of patients, the maximum number of evaluable patients in the two cohorts would be 74. However, in the event that an inevaluable patient is enrolled in each cohort, a total enrollment ceiling of 76 patients will be requested. Our goal is to enroll adenocarcinoma patients, but we do not want to refuse squamous cell carcinoma patients who have no other therapeutic options.

As secondary endpoints, progression free survival and duration of response will also be evaluated, using Kaplan-Meier curves. Progression free survival will be measured from the on-study date until the date of progression or last follow-up if the patient has not progressed. Response duration will be determined beginning at the date a PR or CR is first noted and will last until the patient is noted to have progressive disease relative to the response identified.

Women, 18 years of age or older, from all racial and ethnic backgrounds, will be eligible for the study.

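### Does leaving evaluable undefined in section 5.4.1 unsettle the 0/12 and 4/37 decisions?

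*Combined protocol and SAP*

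**What the plan says.** Section 5.4.1 sets a Simon two-stage design for each histology cohort, with p0 = 5%, p1 = 20% and both error rates at 0.10. Stage 1 reads: "Initially, 12 evaluable patients will be enrolled in each of the two cohorts". With no response the cohort stops; with at least one, "accrual will continue until a total of 37 evaluable patients have been enrolled in that cohort". Four or more responders among the 37 count as activity. The two cohorts need at most 74 evaluable patients, and the ceiling is raised by two: "However, in the event that an inevaluable patient is enrolled in each cohort, a total enrollment ceiling of 76 patients will be requested".

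Section 5.2 opens by limiting response evaluation to patients with measurable disease at baseline. Inclusion criterion 4 in section 2.1.1 requires measurable disease.

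Under Reporting of results, section 5.2 says: "All patients initially considered evaluable will be assessed for response to treatment". Each of these patients goes into one of eight categories, the last being "8) unknown (not assessable, insufficient data". It continues: "All of the patients who met the eligibility criteria and are evaluable, will be included in the main analysis of responses". Then: "Patients in response categories 4-8 will be considered as failing to respond to treatment (disease progression". Then: "All conclusions will be based on all eligible patients". Sub-analyses that leave out early deaths, early discontinuations or major violations are allowed, but may not support conclusions about efficacy.

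**The concern.** Section 5.4.1 does not say what makes a patient evaluable and does not refer to section 5.2. Its two spare places show that some enrolled patients are expected to fall outside the 12 and the 37. Section 5.2 describes the analysis set in two ways, once as eligible and evaluable patients and once as all eligible patients. A patient who is treated but never rescanned could then be a category 8 failure inside the denominator, or an inevaluable patient outside it whose place is refilled.

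The direction of any effect is one-sided. Replacing a non-responder can turn 0/12 into 1/12, or 3/37 into 4/37, but never the reverse. The trial is open-label with a single treatment, so a choice left open could be made with responses known. At stake would be the stage 1 stop, the final verdict for a cohort and the false-positive rate.

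**Working it through.** **1. The plan's own figures.** Inputs from section 5.4.1: 12 patients in stage 1, stop at 0; 37 in total, active at 4 or more; p0 = 0.05, p1 = 0.20.

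- Early stop at p0: 0.95^12 = 0.540 (the plan states 0.54).
- P(active | p) = Σ over x = 1 to 12 of C(12,x) p^x (1−p)^(12−x) × P(Bin(25,p) ≥ 4−x). This gives 0.0935 at p = 0.05 and 0.902 at p = 0.20, both within the planned limits.

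**2. The passages side by side.** Eligibility requires measurable disease, and section 5.2 makes measurable disease at baseline the condition for evaluating response. On that reading every eligible patient is evaluable, so the two descriptions of the analysis set name the same patients. Category 8 then holds patients who were evaluable at the start and later gave insufficient data. They count as failures, and it would be pointless to score them as failures if they were to leave the denominator. The spare places are left for registrations that should not have counted at all.

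**3. Error rates on that reading.** If p0 and p1 are rates among all eligible patients, nothing changes: 0.0935 and 0.902. If they were meant as rates among assessable patients only, the effective rate is p(1−q), where q is the share lost. At q = 1/38, power is 0.892 and the false-positive probability 0.087. At q = 0.087 they are 0.864 and 0.072.

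**4. Loss rates for the other reading.** The plan's allowance is 2/76 = 1/38 = 0.026. Two studies in the background had (46−42)/46 = 0.087 (section 1.2.1, paclitaxel) and (126−113)/126 = 0.103 (section 1.2.4, ixabepilone monotherapy). Applying the last two here is an assumption.

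**5. Unlimited replacement, all-eligible rates.** The rate among counted patients becomes p/(1−q). At p = 0.05:

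- q = 1/38: 0.05/0.9737 = 0.0514, P(active) = 0.1005
- q = 0.087: 0.05/0.913 = 0.0548, P(active) = 0.119
- q = 0.103: 0.05/0.897 = 0.0557, P(active) = 0.125

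These are upper bounds. At q = 0.087 replacement would need 37/0.913 = 40.5 enrolments per cohort, and the plan provides 38. If p0 and p1 are instead rates among assessable patients, unlimited replacement leaves the figures in step 1 as they are.

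**6. One replacement per cohort, as the ceiling provides.** While the spare place is unused, the next counted patient responds with probability p + qp (directly, or as the replacement for a lost patient). Once it is used, the probability is p and further losses count as failures. Carrying the number of responders and the state of the spare place through 12 and then 37 counted patients gives exact results. The counted set always contains every assessable patient who would be counted without replacement. The difference in P(active) is therefore the probability that the two readings end in different decisions.

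| Loss rate q | P(active), p = 0.05 | Difference from 0.0935 | P(active), p = 0.20 | Difference from 0.9024 |
|---|---|---|---|---|
| 1/38 | 0.0981 | 0.0047 | 0.9095 | 0.0071 |
| 0.087 | 0.1016 | 0.0081 | 0.9160 | 0.0136 |
| 0.103 | 0.1019 | 0.0084 | 0.9168 | 0.0144 |

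The 76 is a shared ceiling. If one cohort stops at stage 1, the other could in principle use more spare places, and its figures would lie between steps 5 and 6.

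**The case for a change.** The strongest case for a change is that the rule behind the primary decision should not have to be inferred. No sentence says that evaluability is fixed at baseline. If it means only measurable disease, the words about evaluability in the main-analysis sentence add nothing to eligibility, so a reader may look for a wider meaning. The background summaries use assessable for a subset of treated patients. Any replacement favours continuing, and a sentence of clarification would cost no patients.

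Part of this stands: the term is undefined in section 5.4.1, and a pointer to section 5.2 would be tidier. The rest carries less weight. The background wording reports how other studies were analysed. In the monotherapy trial the 113 was the denominator for the independent radiology rate, while the investigator-assessed rate used all treated patients. One spare place per cohort also suits an occasional faulty registration better than routine replacement: at an assumed 5% loss, the chance of two or more losses among 38 is 0.57. The fear of a choice made after responses are known is limited by section 5.2, which scores not-assessable patients as failures and bars conclusions from analyses that drop early deaths or discontinuations. Whether the agent is active in a cohort is such a conclusion.

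**Conclusion.** No change is called for. The design arithmetic is correct, and section 5.2 supplies the rule that section 5.4.1 leaves unwritten: later losses stay in the 12 and the 37 as non-responders. An analyst who follows section 5.2 reaches a sound decision with the planned error rates.

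The alternative needs two assumptions together, that lost patients are replaced and that p0 is a rate among all eligible patients. Even then, with one replacement per cohort, the false-positive probability stays below 0.10 at the plan's own allowance and passes it by about 0.002 at losses of 8.7% to 10.3%. Decisions differ in about 0.5% to 1.4% of cohorts. The higher values of 0.119 and 0.125 require more enrolments per cohort than the allowance covers.

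These sizes rest on loss rates that the documents do not give for this trial, and on lost patients being non-responders. The baseline reading is an inference from section 5.2 and the entry criteria, though a strong one.

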#### Secondary-

- Assess pharmacodynamic endpoints to determine the extent of tubulin polymerization and whether or not there has been activation of cellular death pathways “distal” to the target.
- Estimate progression free survival and duration of response.

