#### 1.1.2 Secondary:

- Assess pharmacodynamic endpoints after ixabepilone administration to determine the extent of tubulin polymerization and whether or not there has been activation of cellular death pathways “distal” to the target.
- Determine progression free survival and duration of response

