In the randomized, multinational, open-label trial that evaluated the efficacy and safety of ixabepilone plus capecitabine compared to therapy with capecitabine alone, patients had to have previously received an anthracycline and a taxane, had evidence of disease progression or resistance, or, in the case of the anthracycline, received a minimum required cumulative dose. Treatment arms were balanced with regards to prior therapies, disease sites, hormone receptor status and HER2 expression. Patients receiving combination therapy had a statistically significant improvement in progression-free survival (PFS), defined as radiologic progression or death from any cause (hazard ratio 0.69,  $p < 0.0001$ ). The median PFS was 5.7 months in the combination arm and 4.1 months in the capecitabine alone arm. Patients in the combination arm also had an increased objective tumor response rate. Survival data for this trial are to be reported in late 2008. In this trial treatment with ixabepilone caused new or worsening peripheral neuropathy in ~65% of patients treated. Grade 3/4 peripheral neuropathy occurred in 23% of patients treated with ixabepilone and capecitabine. Grade 3/4 peripheral neuropathy was not reported in the capecitabine alone arm. By comparison, in the ixabepilone monotherapy trial, 14% of patients experienced grade 3/4 peripheral neuropathy. With cessation of therapy neuropathy was reversible to grade 1 or better in the majority of patients. Ixabepilone in combination with capecitabine resulted in a 68% incidence of grade 3/4 neutropenia compared to 11% with the capecitabine alone regimen. That ixabepilone was the principal offending agent was supported by a 54% incidence of grade 3/4 neutropenia when ixabepilone was used as monotherapy. Twelve patients receiving ixabepilone with capecitabine died from complications arising from neutropenia. The incidence of neutropenia-associated deaths was higher in patients with moderate or severe hepatic impairment baseline when treated with both ixabepilone and capecitabine. These observations led the FDA to recommend that the combination of capecitabine plus ixabepilone should not be used in patients with moderate or severe hepatic impairment. Other commonly observed toxicities (> 20%) included anemia, leukopenia, thrombocytopenia, fatigue/asthenia, myalgia/arthralgia, alopecia, nausea, vomiting, stomatitis.

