### 3.11 Follow-Up for Progression Free Survival and Duration of Response

An objective of this study is to determine progression free survival and duration of response in patients who achieve either a Complete Response (CR) or a Partial Response (PR). Patients who achieve either a CR or PR and stop receiving study drug will be monitored periodically to follow the course of their response. This follow-up period will vary per patient, but in general will consist of a CT scan every 6 weeks, extending to every 3 to 4 months, per PI discretion. This follow-up may be done here at the NIH Clinical Center, or via the patient's local physician, with scans sent in for inclusion in our trial results. Physical exams, including pelvic exams, will also be done at the same time points.

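### Section 5.4.1 does not count death as a PFS event, so the curve labelled PFS is, as written, time to progression

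*Combined protocol and SAP*

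**What the plan says.** Section 5.4.1 evaluates PFS and duration of response as secondary endpoints with Kaplan-Meier curves. Its whole PFS rule is: "Progression free survival will be measured from the on-study date until the date of progression or last follow-up if the patient has not progressed".

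The plan defines duration of response twice. In 5.4.1 it starts at the first PR or CR and "will last until the patient is noted to have progressive disease relative to the response identified". In 5.2 it runs "until the first date that recurrence or PD is objectively documented". Neither sentence mentions death.

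The objectives put no limit on the PFS population. The Précis has "Estimate progression free survival and duration of response" and 1.1.2 has "Determine progression free survival and duration of response"; the objectives restated in 5.4 are also unrestricted. Section 3.11, however, gives an objective as to "determine progression free survival and duration of response in patients who achieve either a Complete Response (CR) or a Partial Response (PR".

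The background in 1.2.4, reporting a randomized breast cancer trial of ixabepilone plus capecitabine, describes "progression-free survival (PFS), defined as radiologic progression or death from any cause".

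**The concern.** The 5.4.1 rule gives each patient one of two endings: progression, or last follow-up without it. A patient who dies without documented progression falls under the second and is censored. The resulting curve estimates time to progression but carries the PFS label, and a reader would normally take that label to include deaths.

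At stake is how a reported secondary result is read. A median or landmark value from this curve would look at least as favourable as PFS that counts deaths. Two analysts could also report different medians from the same data, one following the written rule and the other following the usual meaning of the term.

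**Working it through.** **Reading the rules side by side**

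| Place | Clock stops at | Death an event? |
|---|---|---|
| 5.4.1, PFS | progression; otherwise last follow-up | no |
| 5.4.1, response duration | progressive disease | no |
| 5.2, response duration | documented recurrence or PD | no |
| 5.2, reporting of results | not a time rule; categories 4-8, including three kinds of early death, count as non-response | only in the response analysis |
| 1.2.4, PFS in another trial | radiologic progression or death | yes, but not a rule for this trial |

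No row makes death an event for PFS or response duration in this trial.

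**Direction.** Take last follow-up to be the date of death. The numbers at risk are then the same whether or not death counts. Each Kaplan-Meier factor is 1 minus events over number at risk, and removing deaths from the events can only leave a factor unchanged or increase it. The curve as written is therefore at or above the curve that counts deaths.

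**Size.** The plan gives no PFS figure to reproduce. Let L be the total hazard of a first event (progression or death), assumed constant, and f the share of first events that are deaths without documented progression. The documents do not give f; the values below are assumptions.

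- Hazard analysed as written: L(1-f).
- True PFS median: ln 2 / L. Median as written: ln 2 / [L(1-f)]. Ratio: 1/(1-f).
- Height of the written curve at the true PFS median: 0.5^(1-f), against 0.5.
- Deaths censored per cohort if every evaluable patient has an event: 12f (cohort stops at stage one) to 37f (full cohort).

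| Assumed f | Median ratio | Curve at true median | Patients per cohort (12f to 37f) |
|---|---|---|---|
| 1% | 1/0.99 = 1.010 | 0.503 | 0.1 to 0.4 |
| 3% | 1/0.97 = 1.031 | 0.511 | 0.4 to 1.1 |
| 5% | 1/0.95 = 1.053 | 0.518 | 0.6 to 1.9 |
| 10% | 1/0.90 = 1.111 | 0.536 | 1.2 to 3.7 |

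To put this in months, borrow the 3.1-month median PFS that 1.2.4 reports for ixabepilone monotherapy in breast cancer, as an illustration only. The written rule would give 3.1/0.99 = 3.13 months at f = 1% and 3.1/0.90 = 3.44 months at f = 10%.

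The documents set no upper limit on f; at 20% the ratio would be 1/0.80 = 1.250. Restaging after cycles 2, 4 and 6, and imaging when treatment stops, make low values plausible. Eligibility down to ECOG 2 and a 3-month life expectancy means that some such deaths can be expected.

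**What does not move.** The decision rules use response counts only. The stated early-termination probability reproduces: 0.95^12 = 0.540, against 0.54 in 5.4.1. No PFS quantity enters it.

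**The case against.** The best defence is that PFS is widely understood to include death, and that 5.2 already treats early deaths as failures. The 5.2 rule, however, classifies patients for the response analysis. It sets no event date, does not reach later deaths, and covers category 8 (unknown) in the same way, so it cannot serve as a PFS event rule. An explicit definition with two endings should not depend on the analyst overriding it.

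It is also fair to say that 1.2.4 describes another trial. It supports the usual meaning of the term but sets no standard that 5.4.1 breaches. And f may be small. Both of these objections stand.

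Four stronger readings are tempting, and the documents do not support them.

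- A reader might infer from 3.11 that PFS will be analysed in responders only. The responder qualifier can attach to duration of response alone, and the Précis, 1.1.2, 5.4 and 5.4.1 are unrestricted. This is loose wording to tidy.
- A reader might infer that non-responders get no imaging after stopping, because 3.11 says "Patients who achieve either a CR or PR and stop receiving study drug will be monitored periodically to follow the course of their response". But 3.9.1 requires imaging for every patient who meets off-treatment criteria, and Appendix B marks staging imaging at study termination. Only later repeat scans are limited to responders. Patients may stop while doing worse or while disease is controlled, so the documents fix neither the direction nor the size of any effect on PFS.
- A reader might infer that the response-duration definitions are contradictory or wrong. Both end at progression (5.2 adds recurrence), and nothing in the documents says that death must end a response. The gap is that the treatment of a responder's death is left unstated.
- A reader might infer that the trial's conclusion is at risk. It rests on response counts, and 3.1 does not list PFS when it names the endpoints.

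**Conclusion.** The point holds, as a minor one. Section 5.4.1 as written censors deaths without documented progression, so its PFS curve is time to progression. That follows from the text. The direction needs only the assumption that such patients are censored at death.

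The size rests on two further assumptions: constant hazards and a value for f. For f between 1% and 10%, the median is overstated by about 1% to 11%, which corresponds to at most about four patients in a full cohort of 37. The same formula applies to response duration, with its own share, if deaths are meant to end a response.

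PFS is secondary, descriptive and tied to no decision rule. The response endpoint, the 0/12 and 4/37 rules and the sample size are untouched.

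**What to change.** In 5.4.1, define PFS as the time from the on-study date to the first documented RECIST progression or death from any cause, whichever comes first. Patients alive without progression are censored at last follow-up. If death is not meant to count, keep the rule and label the endpoint time to progression.

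For consistency, make two small edits alongside:

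- State in both 5.2 and 5.4.1 whether death ends response duration.
- Reword the first sentence of 3.11 so that the responder qualifier clearly applies to response duration, in agreement with the Précis, 1.1.2, 5.4 and 5.4.1.

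The cost is small. Reported medians may be slightly less favourable. Deaths on study are already reported under 7.3.4, but 3.10 says that off-treatment and off-study dates usually coincide, so later deaths would be counted only where known; the report should say so. No change to sample size, decision rules or follow-up schedule is needed.
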